8.2 SAFETY ASSESSMENTS

Monitoring the progress of trials and the safety of participants. The proposed research is a low-risk behavioral trial. Research staff will carefully monitor each participant's emotional reaction during interviews and offer a referral when appropriate. As per ISMMS IRB policies, the PIs are required to notify the IRB promptly of any unanticipated problems involving risks to study participants or others that occur. The PIs and study investigators will monitor the progress of the trial and safety of participants on an ongoing basis. The procedures of this study, such as regular meetings with research staff, will ensure discussion and reporting of all possible outcomes including adverse events. If the adverse event is due to the study and is unexpected, the PIs will draft a safety report and send a copy to the ISMMS IRBs. The IRB committees will serve as an objective review mechanism. This policy/procedure means that any potential conflict of interest inherent in the PIs being the sole reviewers of serious adverse events is avoided. The Data and Safety Monitoring Board (DSMB) meets at least quarterly to review the results of adverse event reporting, protocol deviations, protocol audits and the conduct of the study. Each ISMMS study not otherwise overseen by an external DSMB is reviewed at least annually. The DSMB reports the analysis of their review to Sr. Vice President for Research and to the IRB. To avoid conflicts of interest, members of the DSMB are not involved in the oversight of studies for which they serve as Principal Investigator or Co-Investigator/ biostatistician.

8.3 ADVERSE EVENTS AND SERIOUS ADVERSE EVENTS

Plans for assuring adherence with requirements regarding the reporting of adverse events (AEs) All serious adverse events (AEs) (e.g., medical occurrences resulting in death) that occur during the study defined by the given protocol, regardless of the relation to the research, must be reported to the IRB by telephone, e-mail or fax within 24 hours of the investigator's awareness of the occurrence of the event. The PIs will report AEs to the ISMMS IRB and will disseminate information to other agencies as necessary. These initial reports are followed by a safety report which is a written account of a serious AE determined by a sponsor/investigator to be both related to the treatment under investigation and unexpected in nature. Serious AEs will be summarized annually in the IRB application for continuation or termination of research. All expected non-serious AEs that occur at a greater frequency or severity than anticipated and all unexpected non-serious AEs will be reported to the IRB within 15 working days of the Investigators becoming aware of the event. These AEs are also summarized annually in the IRB application for continuation or termination of the research. Plans for assuring that any action resulting in a temporary or permanent suspension of an NCI funded clinical trial is reported to the NCI grant program director responsible for the grant. [name], Director, Grants and Contracts Office at ISMMS, will provide

Based on "NIH Protocol Template for Behavioral and Social Sciences Research"

20

prompt written notification of any action resulting in a temporary or permanent suspension of this protocol to the NCI grant program director responsible for the grant.

8.4 UNANTICIPATED PROBLEMS

8.4.1 DEFINITION OF UNANTICIPATED PROBLEMS

This protocol uses the definition of Unanticipated Problems as defined by the Office for Human Research Protections (OHRP). OHRP considers unanticipated problems involving risks to participants or others to include, in general, any incident, experience, or outcome that meets all of the following criteria:

- Unexpected in terms of nature, severity, or frequency given (a) the research procedures that are described in the protocol-related documents, such as the IRB-approved research protocol and informed consent document; and (b) the characteristics of the participant population being studied;
- Related or possibly related to participation in the research (“possibly related” means there is a reasonable possibility that the incident, experience, or outcome may have been caused by the procedures involved in the research); and
- Suggests that the research places participants or others at a greater risk of harm (including physical, psychological, economic, or social harm) than was previously known or recognized.

8.4.2 UNANTICIPATED PROBLEMS REPORTING

The investigator will report unanticipated problems (UPs) to the reviewing Institutional Review Board (IRB) and to the Data Coordinating Center (DCC)/lead principal investigator (PI). The UP report will include the following information:

- Protocol identifying information: protocol title and number, PI's name, and the IRB project number
- A detailed description of the event, incident, experience, or outcome
- An explanation of the basis for determining that the event, incident, experience, or outcome represents an UP
- A description of any changes to the protocol or other corrective actions that have been taken or are proposed in response to the UP

To satisfy the requirement for prompt reporting, UPs will be reported using the following timeline:

- UPs that are serious adverse events (SAEs) will be reported to the IRB and to the DCC/study sponsor/funding agency within <insert timeline in accordance with policy> of the investigator becoming aware of the event

Based on “NIH Protocol Template for Behavioral and Social Sciences Research”

- Any other UP will be reported to the IRB and to the DCC/study sponsor/funding agency within <insert timeline in accordance with policy> of the investigator becoming aware of the problem
- All UPs should be reported to appropriate institutional officials (as required by an institution's written reporting procedures), the supporting agency head (or designee), and the Office for Human Research Protections (OHRP) within <insert timeline in accordance with policy> of the IRB's receipt of the report of the problem from the investigator

8.4.3 REPORTING UNANTICIPATED PROBLEMS TO PARTICIPANTS

N/A

9 STATISTICAL CONSIDERATIONS

9.1 STATISTICAL HYPOTHESES

Descriptive statistics will provide summary information about the feasibility of recruitment, acceptability and cultural sensitivity of the program and satisfaction with the program. An arbitrary cutoff value of 80% acceptance will determine the interventions' feasibility for the study. Some parameters include the proportion of eligible participants who are contacted, enrolled, agree, and disagree with the acceptability and cultural sensitivity of the program. Thus, if at least 80% of the participants exceed the previous parameters, the developed program will be determined to be feasible.

- Primary Endpoints:

We hypothesize that we will observe a change in the assessment of mammogram screening intention and knowledge of places where it is possible to obtain a mammogram appointment in the participants who will take part in the pilot test of the culturally adapted intervention (posttest), compared to baseline (pretest).

- Secondary Endpoints:

We hypothesize that we will observe a change in assessment of perceived breast cancer risk and self-efficacy for mammography in the participants who will take part in the pilot test of the culturally adapted intervention (posttest), compared to baseline (pretest).

9.2 SAMPLE SIZE DETERMINATION

We estimate that our sample size of 64 participants will generate a +/- 12% margin of error at a 95% confidence level.

9.3 POPULATIONS FOR ANALYSES

Per-Protocol Analysis Dataset

Based on "NIH Protocol Template for Behavioral and Social Sciences Research"

Descriptive statistics will provide summary information about the feasibility of recruitment, acceptability and cultural sensitivity of the program and satisfaction with the program. An arbitrary cutoff value of 80% acceptance will determine the interventions' feasibility for the study. Some parameters include the proportion of eligible participants who are enrolled, agree, and disagree with the acceptability and cultural relevance of the program. Thus, if at least 80% of the participants exceed the previous parameters, the adapted program will be determined to be feasible and acceptable. To determine program efficacy and sample size estimates for a future intervention, we will use a repeated measures ANOVA to analyze differences in the primary outcomes: screening intentions and HBM constructs (e.g., self-efficacy and perceived risk) immediately before viewing the educational program and immediately after viewing the program. We will conduct univariate and bivariate analyses of the data to provide descriptive summaries of the data, including demographics and responses to primary outcome measures.

We expect only minor amounts of missing data from the surveys and feasibility questionnaires. However, we will examine any patterns of missing data and if needed, consider using missing data imputation methods.

9.4 STATISTICAL ANALYSES

9.4.1 GENERAL APPROACH

For Aim 1 demographic characteristics of the participants will be reported. Data from the quantitative surveys will be analyzed to identify predictors of non-adherence to breast cancer screening. We will conduct univariate and bivariate analyses of the data to provide descriptive summaries of the data, including demographics and responses to primary outcome measures. Data from the audio-recorded in-depth interviews will be transcribed verbatim from audio recordings (using a transcription service). Analyses of the qualitative data will be conducted using the PEN-3 model, which is a method of analyzing data focusing on social processes and actions. The goal of our qualitative research is to identify the unique barriers and facilitators African immigrant women encounter with breast cancer screening. In line with this approach, the coding steps of open coding, axial coding, and selective coding will be used to identify categories and develop properties. Memoing will be conducted throughout the process. A constant comparative method will be used to generate theoretical categories and refine concepts.

For Aim 2, we will conduct univariate and bivariate analyses of the data to provide descriptive summaries of the data, including demographics and responses to primary outcome measures. Independent samples t tests will be used to compare changes in the primary outcomes measures pre-education and post-education. Using a pre-post test design, we will analyze differences in the three primary outcomes: screening intentions, self-efficacy and perceived risk immediately before viewing the educational program and immediately after viewing the program.

To determine program efficacy and sample size estimates for a future intervention, a generalized linear modelling approach will be used with logistic regression. We will use a repeated measures ANOVA to analyze differences in the primary outcomes: screening intentions and HBM constructs (e.g., self-efficacy and perceived risk) immediately before viewing the educational program and immediately after viewing the program. We will conduct univariate and bivariate analyses of the data to provide descriptive summaries of the data, including demographics and responses to primary outcome measures.

Based on "NIH Protocol Template for Behavioral and Social Sciences Research"

23

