4 STUDY DESIGN

4.1 OVERALL DESIGN

The goal of Aim 1 is to collect formative data via a mixed methods approach and use those results to culturally adapt the Witness Project for African immigrant populations. Cultural adaptation will follow the stage model outlined by Barrera et al.⁴⁸ The model includes five stages: 1) information gathering to determine which intervention components to modify; 2) preliminary adaptation design that integrates information from stage 1 to inform preliminary modification of the original intervention; 3) preliminary adaptation tests to pilot the intervention for feasibility and acceptability, 4) adaptation refinement with decisions informed a leadership team/advisory board; and 5) cultural adaptation trial to test the effectiveness of the intervention in changing health outcomes. As this is the first step in this line of research, the proposed study will only follow stages 1-4.

The Witness Project has three main components that will be culturally adapted: 1) educational presentation addressing myths, barriers and values related to breast cancer and mammography, 2) culturally matched, peer led narrative about breast cancer experience, 3) experiential education about breast anatomy and self-examination.

Based on "NIH Protocol Template for Behavioral and Social Sciences Research"

11

The “point of interface” (i.e., merging quantitative and qualitative data) will be associations between mammography screening and HBM constructs (e.g., perceived risk, self-efficacy) and any socio-demographic characteristics (i.e., preferred language, health literacy level). The quantitative results will inform the refinement of the qualitative questions. For example, if an association is found between self-efficacy and screening, we will ask in-depth questions about self-efficacy and suggestions for how it could be improved in this population.

The design chosen for the pilot-test is a one-group pretest –posttest. All of the enrolled participants will receive the same intervention in their preferred language (English or French). To measure the impact of the intervention, will conduct a pre-post assessment of key variables around perceived risk for breast cancer, the intention to complete a mammogram, and self-efficacy related to seeking and completing breast cancer screening. This trial will also assess the feasibility and acceptability of the intervention.

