5.5 STRATEGIES FOR RECRUITMENT AND RETENTION

As indicated in the proposal, human subjects will be recruited for in-depth interviews (N=30) and surveys (N=50), in Aim 1 to understand preferred language, cultural beliefs, access to health care; healthcare engagement, knowledge of breast cancer screening guidelines and predictors of screening behavior. Recruitment will take place within African immigrant communities in New York City.

After incorporating the Aim 1 findings to our existing breast cancer educational program, 64 (n = 32 for English and n = 32 for French speaking) eligible African-born women will be recruited to pilot test the adapted educational program. Participants will be recruited from African immigrant communities in New York City.

Aim 1: Participants will be recruited from the community with the help of our community partner – African Services Committee. Our community partners will help us with our recruitment efforts by advertising the study within their organizations and at events and meetings they may hold for their consumers. Participants will be compensated \$30 to a local store for participating in the research study. In addition, we will promote our study on social media (e.g. WhatsApp groups, Facebook pages) using flyers and video advertisements adapted for online sharing.

Aim 2: Experienced outreach coordinators, assisted by our community partners, will recruit local community, faith-based, and other social organizations to host breast cancer educational programs as we

Based on "NIH Protocol Template for Behavioral and Social Sciences Research"

15

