session and f) completion of the post-program survey including feasibility questionnaire and feedback discussion. After the completion of the question and answer session, participants will be given breast cancer resource guides with local information about how and where to obtain screening. The program will take approximately 90 minutes to complete. Participants will receive an incentive (\$60 gift card) for their participation. Participants will complete a pre-program survey and a post-program survey to assess changes in HBM constructs. The post-program survey will also include a feasibility questionnaire.^{62,63,64,65} The programs will be evaluated using a program summary template that [name] and colleagues have used in previous studies. The summary collects information about the length of the program, number of participants attending the program, gender of program participants, location and site of the program, number of staff and volunteers present, and type of site (faith-based or community-based).

For both in person and virtual educational programs, demographic and pre-post surveys will be primarily collected via RedCap. For virtual programs, participants will be provided with RedCap survey links via chat. For in person programs, participants will be able to complete surveys through RedCap on their own devices or on devices provided by the study team. Hard copies of the surveys will also be available for completion for in person educational programs. All pre and post assessments, collected via RedCap or hard copy of surveys, will be linked only via participant study ID. Assessments will not collect any PHI. They will be anonymous as participant names will not be collected.

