6.1.2 ADMINISTRATION AND/OR DOSING

For Aim 1 of the study, interested individuals will be invited to perform the study activities in a single session, in which they will express informed consent, provide demographic data and complete an in-depth interview or an interviewer-administered survey. Once consented, participants may also complete the demographic questionnaire and/or the interview or survey on another time and/or day of their choice, if so they prefer (i.e., because they feel fatigued; if they have limited continuous availability of time).

For Aim 2 of the study, research staff will focus on sites that include African-born immigrant women 38 years of age and older. A program will be scheduled by the coordinator and individuals at the community sites will be approached to participate in a breast cancer educational program. Some programs will also be held virtually. We will conduct a total of eight programs in English (N=4) and French (N=4). We will recruit a total of 64 eligible women at each program. When recruiting program sites, the Research Assistant will emphasize the language in which the program will be conducted.

The administration of the intervention – including frequency, schedule, setting, and required personnel – will be determined using the input of individuals taking part in Aim 1 of the study.

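### Section 9.4.1 prescribes an unpaired t test for before/after scores from the same women, and nothing ranks it below the repeated measures ANOVA also named

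*Combined protocol and SAP*

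**What the plan says.** Section 9.4.1 gives the Aim 2 comparison as follows: "Independent samples t tests will be used to compare changes in the primary outcomes measures pre-education and post-education". The next sentence lists three outcomes (screening intentions, self-efficacy and perceived risk), measured immediately before and immediately after the program.

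Other sections describe the data:

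- Section 4.1: "The design chosen for the pilot-test is a one-group pretest"–posttest, with every participant receiving the same intervention.
- Section 6.1.1: "All pre and post assessments, collected via RedCap or hard copy of surveys, will be linked only via participant study ID".
- Section 4.4: an Aim 2 participant completes the study by providing both assessments.
- Section 5.5: the sample is "64 (n = 32 for English and n = 32 for French speaking) eligible African-born women". Section 6.1.2 has them attend eight group programs, four in each language.

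Two other methods are named for the same purpose. Section 9.3 says: "To determine program efficacy and sample size estimates for a future intervention, we will use a repeated measures ANOVA". Section 9.4.1 attaches the same opening clause to a different method, "To determine program efficacy and sample size estimates for a future intervention, a generalized linear modelling approach will be used with logistic regression", and then adds: "We will use a repeated measures ANOVA to analyze differences in the primary outcomes".

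**The concern.** An independent-samples t test is valid when the two sets of scores come from different people. Here they come from the same women, so the test ignores the within-woman correlation that a pre/post design exists to exploit. With positive correlation and independent women, its standard error for the mean change is too large, its real type I error falls below the nominal level, and it can miss a modest real change.

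The plan therefore names a wrong method and a suitable one for the same contrast, without an order between them. An analyst could follow either and reach opposite conclusions on the same data. The results also matter beyond the pilot, because sections 9.3 and 9.4.1 say these analyses will inform efficacy and the sample size of a future study. An unpaired analysis does not estimate the SD of change, which a future pre/post calculation would need.

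**Working it through.** **Inputs from the documents.** n = 64, one group, two linked assessments per woman, eight programs (about eight women each, 64/8). The documents give no pre/post correlation (rho), SD, expected shift, within-session correlation or Aim 2 significance level. Everything below that needs these is an assumption: two-sided 0.05, equal SDs before and after, normal scores, a range of rho.

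**The plan's own figure.** Section 9.2 states a margin of error of ±12% at 95% confidence. 1.96 × sqrt(0.25/64) = 12.25%, so it reproduces. It is the precision of a single proportion and does not depend on the choice of t test.

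**Could the sentence mean something else?** An independent-samples test of change scores between the 32 English and 32 French speakers would be legitimate. But the sentence contrasts pre-education with post-education, and section 9.4.6 rules out subgroup analyses. That reading is unlikely.

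**Does another section settle it?** Section 9.3 ties efficacy to the ANOVA, while 9.4.1 ties it to logistic regression. Section 9.4.2 covers logistic regression on screening status and an Aim 1 significance criterion. The amendment history in 10.4 does not mention the t test. None of them ranks the methods.

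**Standard error.** The variance of the mean change is 2·SD²·(1 − rho)/n. The unpaired test assumes 2·SD²/n. The ratio of standard errors is 1/sqrt(1 − rho).

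**An observed shift of 0.3 SD.** Unpaired: t = 0.3/sqrt(2/64) = 1.70 on 126 df, p = 0.092 whatever rho is. Paired: t = 0.3/sqrt(2(1 − rho)/64) on 63 df.

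**Type I error and power.** Simulation with 100,000 trials per cell, independent women, unpaired versus paired:

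| rho | SE overstated by | Paired p at observed 0.3 SD | Real type I error, unpaired | Power at true 0.2 SD | Power at true 0.3 SD |
|---|---|---|---|---|---|
| 0 | 1.00× | 0.095 | 5.0% | 20 vs 20% | 39 vs 39% |
| 0.3 | 1.20× | 0.047 | 2.0% | 16 vs 26% | 37 vs 51% |
| 0.5 | 1.41× | 0.019 | 0.6% | 12 vs 35% | 35 vs 66% |
| 0.7 | 1.83× | 0.003 | 0.06% | 7 vs 53% | 31 vs 86% |
| 0.8 | 2.24× | 0.0003 | below 0.01% | 4 vs 70% | 28 vs 96% |

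At a true shift of 0.5 SD the loss is only 4 to 9 percentage points for rho 0.3 to 0.8.

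**Group sessions.** If changes are correlated within sessions of eight (ICC), the variance of the mean change is multiplied by 1 + 7·ICC. The unpaired test stops being conservative when (1 − rho)(1 + 7·ICC) exceeds 1, that is above ICC = rho/(7(1 − rho)): about 0.06, 0.14, 0.33 and 0.57 for rho 0.3, 0.5, 0.7 and 0.8. Simulated type I error at rho 0.3 and 0.5:

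| ICC | Unpaired, rho 0.3 | Unpaired, rho 0.5 | Paired |
|---|---|---|---|
| 0.05 | 4.5% | 1.8% | about 9% |
| 0.10 | about 7% | about 3.5% | about 13% |

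The unpaired test's real error rate thus depends on two unknowns, and any cancellation is accidental.

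**Form of the outcomes.** In section 3, mammogram intention has five response options, including an unsure one, and mammogram location has three. Neither has a numeric score, so neither the t test nor the ANOVA fits them as collected. Section 9.4.1 omits location from its three outcomes.

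**The case against.** A suitable method is already in the plan: the repeated measures ANOVA appears twice, and for two time points it equals the paired t test. On that view the t-test sentence is a stray line among descriptive analyses. This stands as far as intent goes. It does not remove the conflict, because 9.4.1 moves the efficacy clause to logistic regression and no section says which method prevails.

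The figures above apply at most to self-efficacy and perceived risk. Section 9.4.1 calls them primary outcomes, but the synopsis and sections 3 and 9.1 list them as secondary. This is correct and lowers the weight of the point. Low correlations or large shifts also shrink the loss, and the normal model is only approximate for perceived risk, which is two short rating items.

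Moving to a paired test without allowing for sessions could raise the false-positive rate, as the second table shows. That is true, but session correlation is a separate gap that affects the paired test as well. Relying on one error to offset another is no reason to keep the unpaired test.

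The amendment rationale in 10.4 speaks of intention to be screened within two years, which suggests merging the three affirmative answers. That narrows the coding gap but does not place the unsure answers.

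**Conclusion.** The concern holds. The test prescribed in 9.4.1 is wrong for the design, and nothing in the documents subordinates it to the paired method. For assumed correlations of 0.3 to 0.8 with independent women, it overstates the standard error by 1.20 to 2.24 times and lowers power at a 0.3 SD shift by about 14 to 68 percentage points (51 − 37 to 96 − 28). At zero correlation the two tests nearly coincide, and session correlation could change the direction of the error. The consequence is bounded: the study is a pilot, the scored outcomes are secondary in section 3, and the 80% feasibility rule does not use this test. It should be fixed because the error is plain and the correction is nearly free. The conclusion does not rest on the categorical-item point.

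**What to change.** In 9.4.1, replace the independent-samples t test with a paired t test for the scored outcomes (self-efficacy, and perceived risk if numerically scored). Alternatively, delete the sentence and keep only the two-time-point repeated measures ANOVA. State that this paired analysis governs the pre/post contrast, and align 9.3 with it.

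As a lesser addition, fix before analysis a yes/no coding of the intention and location items, including where unsure answers go, and use a paired binary method such as exact McNemar. If logistic regression is meant for the pre/post contrast, say so and account for the pairing.

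The cost is wording in 9.3 and 9.4.1. The surveys are already linked by study ID, so no extra participants or procedures are needed. The change does not deal with correlation within sessions, which has to be considered separately.
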